12.3 Physical Examination

Physical examination will be performed at screening, at the end of each treatment cycle, and at the EOTV. Descriptive statistics for height (screening only) and weight, and examination of skin, HEENT (head, eyes, ears, nose, and throat), lymph nodes, heart, chest, lungs, abdomen, extremities, and neurologic system, both observed values and changes from baseline (weight) will be summarized.

12.4 Vital Sign Measurements and Performance Status

Evaluation of vital signs includes include blood pressure, heart rate, respirations, pulse oximetry, and temperature at scheduled visits.

Vital sign measurements and Eastern Cooperative Oncology Group (ECOG) will be listed for each patient and by scheduled visit. Descriptive statistics for vital signs and ECOG, both observed values and changes from baseline, will be summarized.

12.5 Electrocardiograms

Twelve-lead ECGs will be obtained according to the schedules outlined in the latest version of the protocol in order to evaluate the potential cardiac effects of study drug, including QT interval prolongation. Recorded values of ECG parameters and change from baseline values will be summarized at each scheduled visit.

In addition, at baseline and maximum post-baseline visits, the proportion of patients having absolute QTc Fridericia value (QTcF) and QTcF interval (Δ QTcF) of the following categories will be presented:

- $\leq 450 \text{ ms}$
- $> 450 \text{ ms to} \le 480 \text{ ms}$
- $> 480 \text{ to} \le 500 \text{ ms}$
- > 500 ms

At maximum post-baseline visits, the proportion of patients who have an increase from baseline in $\Delta QTcF$ of the following categories will be presented:

- $\leq 30 \text{ ms}$
- $> 30 \text{ to} \le 60 \text{ ms}$
- > 60 ms

Central interpretation of ECGs will be used for data analysis purposes and will be summarized by presenting the shift from baseline to worst by cycle. The overall ECG interpretation will be displayed in cross-tabulations by dose cohort.

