    - i. CD4+ count  $\geq$  350 cells/µL,
    - ii. undetectable viral load, and
    - iii. receiving highly active antiretroviral therapy.
  - known history of or current acute or chronic hepatitis B virus (HBV) infection (as evidenced by detectable HBV surface antigen and HBV DNA ≥ 500 IU/mL),
  - d. history of hepatitis C virus (HCV) infection, unless the infection has been treated and cured,
  - e. active SARS-CoV-2 infection. While SARS-CoV-2 testing is not mandatory for study entry, testing for ongoing infection should follow local clinical practice guidelines/standards. Participants with a positive test result for ongoing SARS-CoV-2 infection, known ongoing asymptomatic infection, or suspected ongoing infection are excluded from enrolling in the study. Such patients who are asymptomatic, or become asymptomatic, and who have a subsequent negative SARS-CoV-2 laboratory test may be enrolled.
  - f. Grade 3 or 4 bleeding,
  - g. significant pulmonary compromise including the requirement for supplemental oxygen, history of non-infectious pneumonitis (including radiation pneumonitis), pulmonary fibrosis, or severe chronic obstructive pulmonary disease (COPD),
  - h. uncontrolled (persistent) hypertension (systolic pressure > 180 mm Hg or diastolic pressure > 100 mm Hg),
  - i. clinically significant arrhythmia, or QTcF > 480 msec (ECG to be obtained in triplicate, patient to be excluded if average of 3 readings is > 480 msec),
  - j. unstable angina,
  - k. recent myocardial infarction within 6 months prior to study drug administration (Cycle 1 Day 1),
  - 1. clinically significant heart disease, such as, congestive heart failure, history of pericarditis, myocarditis,
  - m. history of stroke or transient ischemic event within 3 months prior to study drug administration (Cycle 1 Day 1),

- n. untreated pulmonary embolism, or non-catheter-related deep-vein thrombosis in the 3 months prior to study drug administration (Cycle 1 Day 1),
- o. known adrenal insufficiency,
- p. pregnancy, or breast feeding,
- q. major surgery or trauma within 4 weeks before enrollment.
- 12. Known hypersensitivity to murine, yeast, or recombinant proteins; recombinant human serum albumin; benzyl alcohol; or any excipient contained in the flotetuzumab drug formulation.
- 13. Dementia or altered mental status that would preclude sufficient understanding to provide informed consent.

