## 7.7 Electrocardiography and Continuous Telemetry Monitoring

Twelve-lead ECGs will be obtained according to **Appendix 1** to evaluate the potential cardiac effect, including QTc interval prolongation. There are no requirements for fasting and no restrictions for fluid and food intake by the patients during the study, although it is recommended that, to the extent possible, ECGs be obtained pre-meal.

To account for intrinsic variability, screening and Cycle 1 Day 15 (or when patient has reached 500 ng/kg/day dose level, if later than Cycle 1 Day 15) ECGs should be obtained in triplicate (3 ECGs per time point at approximately 1-minute intervals). Subsequent ECGs will be performed when clinically indicated, and will be single tracing unless clinical circumstances, and at the discretion of the investigator, indicate otherwise. Central interpretation of ECGs will be used for data analysis purposes.

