7 STATISTICAL METHODOLOGY

7.1 General Considerations

Safety and efficacy summaries will be provided for each dose level cohort.

Unless otherwise specified, the following general considerations are applied in data analyses:

- All statistical tests will preserve a significance level of 0.05 for two-sided tests, unless otherwise specified.
- The baseline value is defined as the latest value at the time of or prior to the first dose of study treatment.
- Categorical data will be summarized by the number and percent of patients falling within each category.
- Continuous variables will be summarized by descriptive statistics, including mean, standard deviation, median, minimum, and maximum.
- Time-to-event endpoints will be summarized by the number and percent of the event, median time and corresponding 95% confidence interval (CI), and event free rate and corresponding 95% CI at the specified time points of interest.
- To summarize safety/efficacy data by visit, the post-baseline results will be summarized by the scheduled visit or the derived visit as appropriate.
- In general, the derived visit is the same as the scheduled visit in the protocol which is defined by study day; data that is closest to derived visit (before and after) will be used as the value for that visit. In case that two data collected at the equal distance to the derived visit, the later one will be used.
- Summaries in the Safety Population will be reported by dose cohort and total population; summaries in the Efficacy Population will be reported by PIF, ER and the combined PIF/ER total population.
- The impact of COVID-19 may be assessed and analyzed on a case by case basis. In particular, the following analyses may be performed if there are enough COVID-19 positive patients to render the analyses meaningful:
 - Number of patients discontinued study treatment and/or discontinued from study due to COVID-19, if such reason is collected
 - o Summary of tumor response, PFS and OS
 - Summary of study drug interruption, delay or withdraw due to COVID-19, if such reason is collected
 - Listing of protocol deviation due to COVID-19 separately

• All data summaries and tabulations will be conducted using SAS® software Version 9.3 or higher.

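### SAP 12.5 has no rule for combining triplicate ECGs, so the SAP 7.1 defaults keep one tracing of three, and it attaches the absolute QTcF limits to the change from baseline

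*SAP*

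**What the plan says.** **Collection.** Protocol 7.7 gives the reason for replicates: "To account for intrinsic variability, screening and Cycle 1 Day 15" ECGs (or the ECG on reaching 500 ng/kg/day, if that is later) are taken three times, roughly one minute apart. Any other ECG is done when clinically indicated and is normally a single tracing. Appendix 1 repeats this.

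**Eligibility.** Protocol 5.2, criterion 11i, works on the mean: "patient to be excluded if average of 3 readings is > 480 msec".

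**SAP defaults.** SAP 7.1 opens its list with "Unless otherwise specified, the following general considerations are applied in data analyses". Three of its rules matter here:
- Baseline: "The baseline value is defined as the latest value at the time of or prior to the first dose of study treatment".
- Visit value: "data that is closest to derived visit (before and after) will be used as the value for that visit".
- Ties: "In case that two data collected at the equal distance to the derived visit, the later one will be used".

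**SAP QT tables.** SAP 12.5 does not mention triplicates or averaging and does not override these rules. Its first outlier table covers, "at baseline and maximum post-baseline visits, the proportion of patients having absolute QTc Fridericia value (QTcF) and QTcF interval", the last item being labelled ΔQTcF, under a single list with cut-points at 450, 480 and 500 ms. Its second covers "the proportion of patients who have an increase from baseline in" ΔQTcF, with cut-points at 30 and 60 ms.

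**The concern.** There are two separate defects.

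1. **Replicates.** The protocol collects three tracings because one is noisy, and it uses their mean to decide who enters. The SAP then has no averaging step, and its general rules, applied as they stand, choose one tracing. The precision gained by collecting triplicates is lost at the analysis stage, and two programmers could derive different QTcF values from the same data.

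2. **Table limits.** Cut-points meant for a QTcF level are attached to a change, and cut-points meant for a change are attached to an increase in that change.

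Protocol 9.5.3 singles out QT prolongation as the main purpose of the ECG analysis, and Cycle 1 Day 15 is the only scheduled on-treatment ECG in Appendix 1. The outlier tables therefore lean heavily on one pair of triplicates. Noisier values can push patients over a limit by chance, and a mislabelled row tells the reader nothing.

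**Working it through.** **Figure to reproduce.** Neither document states an error rate, power or precision for QTc, so there is none. The check is a reading of the rules followed by an illustration.

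**Step 1: apply the rules to a triplicate.**
- Baseline: three screening tracings, all before first dose. The latest is the third, so baseline is one tracing.
- Cycle 1 Day 15: SAP 7.1 defines derived visits by study day. If distance is counted in days, the three tracings are equally close and the tie rule keeps the last.
- Result: one tracing minus one tracing, where the protocol's own eligibility rule would use a mean of three.

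**Step 2: apply the table wording.**
- ΔQTcF at baseline is baseline minus baseline, which is 0 for everyone.
- After baseline, essentially every ΔQTcF is at or below 450 ms, so those rows carry no information.
- The 30/60 ms table, as worded, is a change of ΔQTcF from its own baseline, a change of a change. The limits have their usual meaning only for post-baseline QTcF minus baseline QTcF.
- No assumption is needed for this step.

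**Step 3: effect of not averaging.** Let s be the within-session SD of a single QTcF reading. The documents do not give it, so s = 5, 8, 10 and 15 ms are assumed. Errors are taken as normal and independent, with no true change and no between-session variation.
- One tracing minus one tracing: SD of change = s√2.
- Mean of three minus mean of three: SD of change = s√(2/3).
- Ratio: √3 = 1.73 for any s.
- P(false increase > 30 ms) = 1 − Φ(30/SD).

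| s (ms) | SD, single (ms) | SD, means (ms) | P(>30), single | P(>30), means |
|---|---|---|---|---|
| 5 | 7.1 | 4.1 | 0.0% | 0.0% |
| 8 | 11.3 | 6.5 | 0.4% | <0.01% |
| 10 | 14.1 | 8.2 | 1.7% | 0.01% |
| 15 | 21.2 | 12.2 | 7.9% | 0.7% |

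Absolute limits are affected too. For a patient whose true QTcF is 470 ms, the chance of being counted above 480 ms is 1 − Φ(10/s) with one tracing and 1 − Φ(10√3/s) with a mean of three: 2.3% against <0.1% (s = 5), 10.6% against 1.5% (s = 8), 15.9% against 4.2% (s = 10), and 25.2% against 12.4% (s = 15).

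**Step 4: add between-session variation.** Tracings a minute apart share whatever differs between screening and Day 15, and averaging does not remove that. Take s = 10 ms and an assumed between-session SD of 10 ms.
- Single: SD = √(2·100 + 2·100) = 20.0 ms; P(>30) = 1 − Φ(1.50) = 6.7%.
- Means: SD = √(2·100 + 2·100/3) = 16.3 ms; P(>30) = 1 − Φ(1.84) = 3.3%.

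The contrast becomes two-fold. The 1.73 ratio applies only to the within-session part of the SD.

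**The case against.** **The SAP never tells anyone to use a single ECG.** This is true. The visit rule is the closest value, with the later one only on ties, and it reads naturally as choosing between assessments on either side of a visit. Protocol 7.7 treats the three tracings as belonging to one time point. Central vendors manage the ECG data (Protocol 10.3), central interpretation is used for analysis, and programming conventions are left to a separate programming plan that is not among the documents (SAP 14). The value delivered may already be a mean. This limits the point to a gap that the default rules fill badly. It does not close the gap, because neither document says that a mean is used, and a programming plan should implement the SAP's definition of a value rather than supply it.

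**The intended tables can be guessed.** This also stands in part. Absolute QTcF is in the first table with the right limits, and the 30/60 ms limits are present for an increase. A reader might infer that the QTc outlier counts will be wrong. The documents do not support that: the ΔQTcF rows are uninformative and the second label is faulty, but the absolute counts are usable, and the increase counts are too once the label is read as QTcF.

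**Larger effects are tempting.** A reader might take the maximum post-baseline value as the largest of three tracings and derive an upward bias of about 0.85s, or 4 to 13 ms for s of 5 to 15 ms. SAP 12.5 refers to maximum post-baseline visits, and the SAP 7.1 rules give one value per visit, so that bias does not follow from the text. Nor should a false-positive rate be multiplied by 170. That is the efficacy sample, whereas safety tables use everyone dosed (47 in escalation plus about 283 planned in expansion), and not all of them will have a Day 15 triplicate.

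**These tables are not the whole QT assessment.** Correct. SAP 12.5 also plans recorded values and changes by scheduled visit, the shift from baseline to worst by cycle, and overall interpretation by dose cohort.

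**Conclusion.** Two things hold. First, the limits in SAP 12.5 are wrong as written: level cut-points are applied to ΔQTcF, including at baseline where it is zero, and the change cut-points are applied to an increase in ΔQTcF. This rests on the text alone. Second, there is no rule for combining triplicates, and the SAP 7.1 defaults, read literally, keep one tracing of three. Averaging would be a free improvement.

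The size of the second part is a 1.73-fold larger within-session component of the SD of QTcF change, given independent within-session errors. The consequence for false increases above 30 ms depends on SDs that the documents do not give: about 0% to 8% for single tracings against 0% to 0.7% for means over an assumed s of 5 to 15 ms, and a smaller relative contrast once between-session variation is added. The gain arises only at the two triplicate time points.

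Severity is minor. The tables are descriptive, no test or stopping boundary uses them, and the primary CR/CRh analysis is unaffected.

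**What to change.** In SAP 12.5, stated as overriding SAP 7.1 for ECGs:

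1. At each triplicate time point, the QTcF value is the mean of the available replicates, for baseline and post-baseline alike.
2. The maximum post-baseline value is taken over time-point values. Single unscheduled tracings enter as they are and are flagged.
3. The 450/480/500 ms categories apply to absolute QTcF only.
4. The 30/60 ms categories apply to ΔQTcF, defined as post-baseline QTcF minus baseline QTcF.

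It is also worth confirming with the central ECG vendor whether individual readings or means are transferred, so that the programming matches.

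The cost is a short SAP edit and a few lines of programming. The tracings are already being collected, so no new data and no protocol amendment are needed.

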12.6 Left Ventricular Ejection Fraction

If the patient has a history or signs and symptoms of cardiac disease, an echocardiogram (or multiple-gated acquisition scan [MUGA] if indicated) will be obtained during the screening period, if one was not performed within 30 days before the start of treatment (Cycle 1 Day 1). An echocardiogram (or MUGA if indicated) may also be conducted during the study if clinically indicated. A listing will be provided at patient level.

12.7 Pulmonary Function Testing

PFT, including DLCO and FEV1, will be conducted during the screening period if testing was not performed within 30 days before the start of treatment (Cycle 1 Day 1). PFT may also be conducted during the study if clinically indicated. listings will be provided at patient level.

• During the COVID-19 pandemic, if PFT equipment is not available, a correlative stair-climbing test may be conducted instead, together with lung CT and echocardiogram irrespective of cardiac history. The patient must pass the stair-climbing test, with O_2 saturation \geq 95%, lung CT with normal appearing lung parenchyma, and normal echocardiogram

13 INTERIM ANALYSIS

13.1 General Information

Following a three-stage design, the interim analyses will be performed after 40 and 100 patients have been enrolled and either have had their responses evaluated or discontinued for any reason from study treatment prior to their first response assessments. The first interim analysis is for futility only and the second interim analysis is for both futility and efficacy. See Section 4.2 for more details.

13.2 Data Safety Monitor (DSM)

Prior to Protocol Amendment 13, an independent DSM (with disease-specific and/or immunotherapy expertise) was involved in all decisions regarding transition from the Single Patient Dose Escalation Segment to the Multi-patient Dose Escalation Segment and regarding the definition of MTDS and transition to the MTDS Cohort Expansion Segment of the study. In the Single Patient Dose Escalation Segment, safety data from all patients followed through Study Day 28 (Cycle 2 Day 1) was reviewed. Safety data from each dose escalation cohort in the Multi-patient Dose Escalation Segment was made available to the DSM after each cohort of patients had been followed for a minimum of 28 Study Days.

Safety evaluations was conducted on an ongoing basis during the Cohort Expansion Segment of the study. Review by Principal Investigators (or designee), the Medical Monitor and the DSM was conducted in regular intervals. The interval analysis utilized data from all cycles of treatment. If during the conduct of the interval cohort analysis, the Bayesian posterior probability is greater than 80% that the DLT event rate is more than 20%, enrollment would be paused and an ad hoc meeting of the Principal Investigators (or designee), the Medical Monitor, and the DSM would be held to consider dose reduction or study termination.

13.3 Independent Data Monitoring Committee

Starting with Protocol Amendment 13, an independent data monitoring committee (IDMC) is formed to conduct regular independent safety review. This replaces the independent DSM in place prior to this amendment.

At each IDMC safety review meeting, IDMC will receive and review aggregate safety data. The IDMC will determine whether the enrollment should be paused based on Bayesian posterior probability evaluation of DLT event rate. This posterior probability is calculated based on the following Bayesian binomial model: Suppose that the DLT rate p follows non-informative prior Beta(1,1), and that r out of n treated patients have experienced DLTs, then the posterior distribution for p is Beta(1+r, 1+n-r). Then, for each n in 8 patient segments, the number of patients with DLTs that would result in a pause of enrollment is the smallest integer r, satisfying P(p>20%|n, r)>80%, where $p\simBeta(1+r, 1+n-r)$. Table 5 below shows the number of patients with DLTs that would result in a pause of enrollment to assess toxicity.

Table 5	Stopping Bounds for Excess Toxicity Based on Bayesian Beta
	Binomial Model with Beta (1,1) Prior

Number of patients treated (n)	Number of patients with DLTs that would result in a pause of enrollment (r)	
8	3	
16	5	
24	7	
32	9	
40	10	
48	12	
56	14	
64	16	
72	17	
80	19	
88	21	
94	22	

The IDMC will also hold a minimum of two safety and efficacy review meetings for two planned interim analyses (additional ad hoc meetings will be held as needed). At each meeting, in addition to above safety evaluation, IDMC will also receive and review aggregate efficacy data to determine whether enrollment should continue based on futility and efficacy boundaries described in Section 4.2. The details of IDMC formation and meeting conduct is described in a the **IDMC Charter**.

13.4 Statistical Approaches for Control of Alpha

The type I error rate will be controlled at the overall one-sided 0.025 level by using 3-stage design. The decision rules are as follows:

First stage: the study enrollment will continue if at least 5 (12.5%) out of 40 patients have response of CR/CRh.

Second stage: the study enrollment will continue if at least 15 (15%) out of 100 patients have response of CR/CRh.

Claim success if at least 25 (25%) out of 100 patients have response of CR/CRh at the second stage or at least 35 (20.6%) out of the total of 170 patients have response of CR/CRh at the final stage.

The 3-stage design yields a 1-sided alpha of 0.005 for the efficacy boundary at the second interim analysis and an overall 1-sided alpha of 0.024 with approximately 80% power at the final analysis. The probability of early termination under H0 (futility) in the first two stages is 55%.

14 LIST OF TABLES, LISTINGS, AND FIGURES

The list of tables, listings, and figures (TLFs) and associated shells planned for the clinical study report based on the analyses described in this SAP will be provided in a separate SPP, which will also include data reporting conventions and programming specifications for the development of these TLFs.

Appendix 1International Working Group (IWG) Response Criteria for Acute Myeloid Leukemia
(AML) Modified for Assessment of AML in this Study

Response Criterion	Time of Assessment	Neutrophils* (μL)	Platelets* (μL)	Bone Marrow Blasts (%)	Other
Complete Remission (CR)	Day 25 + 3 days (each cycle)	≥ 1,000	≥ 100,000	< 5	Transfusion [#] Extramedullary disease (EMD)
• Morphologic CR (mCR)	Day 25 + 3 days (each cycle)	≥ 1,000	≥ 100,000	< 5	Transfusion [#] EMD
• Cytogenetic CR (CRc)	Day 25 + 3 days (each cycle)	≥ 1,000	≥ 100,000	< 5	Cytogenics – normal, EMD
• Molecular CR (CRm)	Day 25 + 3 days (each cycle)	≥ 1,000	≥ 100,000	< 5	Molecular – negative, EMD
CR with partial hematologic recovery (CRh)	Day 25 + 3 days (each cycle)	≥ 500	≥ 50,000	< 5	Transfusion ^{\$} EMD
CR with incomplete blood count recovery (CRi)	Day 25 + 3 days (each cycle)	< 1,000	< 100,000	< 5	Transfusion ^{\$} EMD
• CR with incomplete neutrophil recovery (CRn)	Day 25 + 3 days (each cycle)	< 1,000	≥ 100,000	< 5	Transfusion [§] EMD
• CR with incomplete platelet recovery (CRp)	Day 25 + 3 days (each cycle)	≥ 1,000	< 100,000	< 5	Transfusion ^{\$} EMD
Morphologic leukemia-free state (MLFS)	Day 25 + 3 days (each cycle)	NA	NA	< 5	EMD
Partial remission (PR)	Day 25 + 3 days (each cycle)	> 1,000	> 100,000	> 50% decrease or decrease to 5-25	Blasts < 5% if Auer rod positive
Other benefit (OB)	Day 25 + 3 days (each cycle)	NA	NA	> 30% decrease	NA

Flotetuzumab

CP-MGD006-01: Statistical Analysis Plan

Response Criterion	Time of Assessment	Neutrophils* (µL)	Platelets* (μL)	Bone Marrow Blasts (%)	Other
Stable disease (SD)	Day 25 + 3 days (each cycle)	NA	NA	Absence of CR, CRh, CRi, PR, MLFS, OB, and criteria for PD not met	NA
Progressive disease	NA	NA	NA	 Evidence for an increase in bone marrow blast percentage and/or increase of absolute blast counts in the blood: > 50% increase in marrow blasts over baseline (a minimum 15% point increase is required in cases with < 30% blasts at baseline; or persistent marrow blast percentage of > 70% over at least 3 mo; without at least a 100% improvement in ANC to an absolute level (>0.5 x 10%/L [500/mL], and/or platelet count to >50 x 10%/L [50 000/mL] non-transfused); or > 50% increase in peripheral blasts (WBC x % blasts) to > 25 x 10%/L (> 25 000/mL) (in the absence of differentiation syndrome)†; or New extramedullary disease 	In general, at least 2 cycles of flotetuzumab should be administered to determine "progressive disease". "Progressive disease" is usually accompanied by a decline in ANC and platelets, increased transfusion requirement, and decline in performance status or increase in symptoms
Recurrence/relapse	Relapse after CR is defined as a reappearance of leukemic blasts in the peripheral blood and \geq 5% blasts in the bone marrow not attributable to any other cause (e.g., bone marrow regeneration after consolidation therapy)				

CR = complete remission (includes mCR, CRc, CRm).

 $CRi = includes neutrophil count \ge 1000 \text{ or platelet count} \ge 100,000.$

*Assessment is quantitated by BM biopsy and best CBC (up to 28 days post BM biopsy).

[#] No RBC and/or platelet transfusion within 5 days prior to response assessment.

^{\$} No platelet transfusion within 5 days prior to response assessment

† Certain targeted therapies, for example, those inhibiting mutant IDH proteins, may cause a differentiation syndrome, that is, a transient increase in the percentage of bone marrow blasts and an absolute increase in blood blasts; in the setting of therapy with such compounds, an increase in blasts may not necessarily indicate PD.
